## Protocol History

Protocol History	
Version and Date of Protocol	Comments
Version 1.0 (05-MAY-2020)	Original Version Submitted to FDA
Version 1.1 (29-JUN-2020)	Updated Version Submitted to FDA
Version 1.2 (20-OCT-2020)	Urine collection, phlebotomy and dressing viral shedding collection minimized
Version 1.3 (10-DEC-2020)	Matched Wounds capped at one (1) pair and Secondary Unmatched Wounds capped at four (4).
Version 1.4 (21-APR-2021)	Updated statistical plan and additional details on study assessments

## Key Changes in the Protocol

Major changes to the protocol are summarized below. Minor administrative changes involving formatting, grammar, syntax, punctuation, and other editorial changes are not summarized in the table below.

Change and Rationale	Affected Sections

Statistical analysis for primary and key secondary endpoint measurement will be analyzed using the McNemar Test, adjusted per FDA agreement. Furthermore, the primary endpoint is defined as wounds that meet any of the following conditions:
 
 
• Healed on Week 22 and Week 24, or
 
• Healed on Week 24 and Week 26.
 
 
The secondary key endpoint is defined as wounds that meet any of the following conditions:
 
 
• Healed on Week 8 and Week 10, or
 
• Healed on Week 10 and Week 12.
 
 
Only wounds that are healed for at least two (2) consecutive weeks are counted as positive responses.
	
Synopsis; Section 2.2; Section 6.2; Section 8.1; Section 8.2; and Section 8.7

The protocol has been amended to add clarification around the assessment of the Primary Wounds, such that only the originally selected area at the Week 1 Visit, will be assessed at the Week 8, 10, 12, 22, 24 and 26 Visits. The neighboring wounds which have received treatment during the study will not be included in this assessment.
	
Section 2.2; Section 4.2; Section 5.1; Section 6.2; Section 8.1; Section 8.2; and Section 8.7

Per Agency's recommendation, a McNemar Test has been used for sample size calculation. In the Phase I/II study, the response rates for Weeks 8 through 12 were from 70-100% for wounds randomized to B-VEC and 0-33% for wounds randomized to placebo, respectively. Therefore, the sample size has been revised to 24 subjects assuming a response rate of 75% among wounds randomized to B-VEC and a response rate of 25% among wounds randomized to placebo. With 90% power and a two-sided Type 1 error rate of 5%, 24 subjects (i.e., 24 wound pairs) are required.
	
Synopsis; Section 3.0; and Section 8.3

## Protocol Synopsis

Title	GEM-3: A Phase III Double Blinded, Placebo-Controlled, Efficacy and Safety Study of Beremagene Geperpavec (B-VEC, previously "KB103") for the treatment of Dystrophic Epidermolysis Bullosa (DEB)																
Study Number	B-VEC-03																
Number of Subjects	Approximately 24 subjects																
Study Phase	Phase III study																
Number of Centers	3 centers																
Study Objectives	The primary objective is to determine whether administration of B-VEC in addition to standard of care improves wound healing as compared to placebo in children, adolescents, and adults with Dystrophic Epidermolysis Bullosa (DEB).																
Study Design	
GEM-3 is a multi-center, intra-subject randomized, placebo-controlled, double blinded, Phase III study of B-VEC for the topical treatment of DEB wounds. Each subject will serve as their own control.
 
Definition of Unit Dose: Unit dose varies by wound area
 
  
 Wound Area*	Unit Dose	
   
 <20 cm^2	4×10^8 PFU/wound	
 
 20 to 40 cm^2	8×10^8 PFU/wound	
 
 40 to 60 cm^2	1.2×10^9 PFU/wound	
  
 
* Wound area determined by the Investigator using the validated Canfield photography quantitation at Week 1. Subsequent Secondary Wounds not selected at Week 1, will have the wound area determined during selection.
 
Definitions:
 
Weekly Treatment: 1 unit-dose of B-VEC or placebo
 
Treatment Cycle: Weekly Treatment until complete wound closure of wounds selected at baseline and any new surrounding wounds (neighboring wounds) during the treatment phase.
 
Maximum Weekly Dose per subject:
 
  
 Age	Maximum Weekly Dose	
   
 ≥ 6 months to < 3 years	1.6×10^9 PFU/week	
 
 ≥ 3 years to < 6 years	2.4×10^9 PFU/week	
 
 ≥ 6 years	3.2×10^9 PFU/week	
  
 
Matched Wounds: Two matched wounds similar in size, located in similar anatomical regions, and have similar appearance.
 
Two matched wounds in a 1:1 ratio per subject will be selected to evaluate the primary and secondary endpoints. The matched wounds will be randomized, such that one wound will receive Weekly
	Wound Area*	Unit Dose	<20 cm 	4×10  PFU/wound	20 to 40 cm 	8×10  PFU/wound	40 to 60 cm 	1.2×10  PFU/wound	Age	Maximum Weekly Dose	≥ 6 months to < 3 years	1.6×10  PFU/week	≥ 3 years to < 6 years	2.4×10  PFU/week	≥ 6 years	3.2×10  PFU/week
Wound Area*	Unit Dose																
<20 cm 	4×10  PFU/wound																
20 to 40 cm 	8×10  PFU/wound																
40 to 60 cm 	1.2×10  PFU/wound																
Age	Maximum Weekly Dose																
≥ 6 months to < 3 years	1.6×10  PFU/week																
≥ 3 years to < 6 years	2.4×10  PFU/week																
≥ 6 years	3.2×10  PFU/week																

	
Treatment of B-VEC and one wound will receive Weekly Treatment of placebo for a Treatment Cycle.


Study Design (continued)
	
Remaining Weekly Dose: The difference between Maximum Weekly Dose per subject per week and the sum total of the B-VEC Dose(s) applied to the Primary Wound Pair per subject per week. The Remaining Weekly Dose will be used to treat Secondary Wounds. Up to four (4) Secondary Wounds may be selected.
 
For example: If a subject 7 years of age, presents with the primary wound pair <math>\leq 20\text{cm}^2</math> then the Remaining Weekly Dose during a weekly visit = Difference of <math>(3.2 \times 10^9 \text{ PFU} - (4 \times 10^8 \text{ PFU})) = 2.8 \times 10^9 \text{ PFU/subject/week}</math>. The Remaining Weekly Dose will be applied to secondary wounds for monitoring safety and efficacy.
 
Re-dosing regimen
 
During the study, if a neighboring wound near the primary wound opens up, (approximately 2-3 cm from the original wound) that wound may receive treatment at the discretion of the Investigator. When a matched primary wound and its neighboring wound/s close completely, as determined by the Investigator during a weekly visit, then no treatment will occur. Weekly treatment on that wound will resume when the originally selected wound or its neighboring wound/s is determined to be open by the Investigator at a weekly visit.
 
The re-dosing regimen will be followed throughout the study.
 
Secondary Wounds
 
The Remaining Weekly Dose calculated during a weekly visit will be applied to a maximum of four (4) additional wounds (“Secondary Wounds”). Secondary Wound(s) will receive a Weekly Treatment of B-VEC for the Treatment Cycle. The number of Secondary Wounds treated will depend on wound area of the Secondary Wound(s). The total dose applied to Secondary Wounds is not to exceed the Remaining Weekly Dose. During the study, if a neighboring wound near the Secondary wound opens up, (approximately 2-3 cm from the original wound) that wound may receive treatment. When the secondary wound and the neighboring wound close completely, as determined by the Investigator during a weekly visit, then that particular wound will stop receiving treatment. For Secondary Wounds, avoid selecting wounds that are in close proximity to the Primary Wound Pair.


Primary Endpoint
	
Wound Healing
 
The primary endpoint is the proportion of DEB primary wound sites with complete wound healing of the originally selected baseline wound in B-VEC versus placebo treated intra-subject wound sites at Weeks 22 and 24 or Weeks 24 and 26, as determined by the Investigator, to evaluate durability and repeat dosing. The complete wound healing is defined as 100% wound closure of the exact original wound surface area selected at baseline, specified as skin re-epithelialization without drainage.

Secondary Endpoints
	
Key Secondary Endpoint
 
 
• Proportion of the selected primary wound sites with complete wound healing of the exact wound surface area selected at baseline (as defined in the primary endpoint) in B-VEC-treated versus placebo at Weeks 8 and 10 or Weeks 10 and 12 (as determined by the Investigator) to evaluate durability.
 
 
Secondary Endpoint
 
 
• The mean change in pain severity using a VAS score per primary wound site associated with wound dressing changes at Weeks 22, 24 and 26 for each treated versus placebo wound, for ages 6 and above on the primary wound pair. For ages below 6 years, the Face Legs Activity Cry and Consolability-Revised (FLACC-R) scale will be used.
 

Exploratory Endpoints
	
 
• Relative time to wound closure from baseline.
 
• Duration of closure, as defined by the time from complete wound closure to the reopening of the Primary Wounds.
 
• The mean change in Quality of Life in addition to Skindex score as compared to baseline at Week 26.
 

Safety Endpoint
	
 
• The safety and tolerability of B-VEC based on the assessment of adverse events, physical examinations, vital signs, and clinical laboratory test results.
 


Subject Population
	
Inclusion Criteria
 
 
1. The subject or legally appointed and authorized representative must have read, understood and signed an Institutional Review Board/Ethics Committee (IRB/EC) approved Informed Consent or Assent Form and must be able to and willing to follow study procedures and instructions.
 
2. Age <math>\geq</math> 6 months and older at the time of Informed Consent.
 
3. Clinical diagnosis of the Dystrophic Epidermolysis Bullosa.
 
4. Confirmation of DEB diagnosis (either DDEB or RDEB) by genetic testing including COL7A1.
 
5. Two (2) cutaneous wounds meeting the following criteria: 
 
a. Location: similar in size, located in similar anatomical regions, and have similar appearance (Refer to Section 5.8 for more details).
 
b. Appearance: clean with adequate granulation tissue, excellent vascularization, and do not appear infected.
 
 
 
6. Subjects and caregivers who, in the opinion of the Investigator, are able to understand the study, co-operate with the study procedures, and are willing to return to the clinic for all the required visits.
 
7. Male or Female of childbearing potential must use a reliable birth control method throughout the duration of the study and for 3 months post the last treatment. Refer to Section 4.5.1 for more details.
 
8. Negative Pregnancy test on Visit 1 (Week 1), if applicable.
 

	
Exclusion Criteria
 

1. Medical instability limiting ability to travel to the Investigative Center.

2. Diseases or conditions that could interfere with the assessment of safety and efficacy of the study treatment and compliance of the subject with study visits/procedures, as determined by the Investigator.

3. Current evidence or a history of squamous cell carcinoma in the area that will undergo treatment.

4. Subject's actively receiving chemotherapy or immunotherapy at Visit 1 (Week 1)

5. Active drug or alcohol addiction as determined by the Investigator.

6. Hypersensitivity to local anesthesia (lidocaine/prilocaine cream).

7. Participation in an interventional clinical trial within the past three (3) months (not including B-VEC administration).

8. Receipt of a skin graft in the past three (3) months.

9. Pregnant or nursing women.

--	--


Study Treatment, Duration and Assessments
	
Study Treatment
 
Week 1
 
 
- Following randomization of the matched primary wound pair, wounds will receive one Weekly Treatment in a double-blinded manner.
 
- The Remaining Weekly Dose will be calculated and applied to a maximum of four (4) additional wounds (“Secondary Wounds”). Secondary Wound(s) will receive a Weekly Treatment of B-VEC. The number of Secondary Wound(s) treated will depend on wound area of the Secondary Wound(s). The total dose applied to Secondary Wound(s) is not to exceed the Remaining Weekly Dose.
 
 
Week 2 through 26
 
 
- Subjects will return to the clinical site for assessment of all wounds by the Investigator.
 
- The Primary Wound Pair will receive one Weekly Treatment in a double-blinded manner. However, if one of the wounds in a matched Primary Wound Pair closes completely and there are no open neighboring wounds, as determined by the Investigator during a weekly visit, then that particular wound and its neighboring wound/s will not receive Weekly Treatment that week. Once that particular wound, or its neighboring wound/s, is determined to be open by the Investigator at a weekly visit, Weekly Treatment will continue. If the originally selected primary wound closes, its neighboring wound/s may continue to receive treatment.
 
- If a Secondary Wound is closed completely, as well as its neighboring wound/s, as determined by an Investigator, during a weekly visit, then that particular wound and its neighboring wound/s will not receive Weekly Treatment that week. If the originally selected secondary wound closes, its neighboring wound/s may continue to receive treatment. The total dose applied to secondary wounds is not to exceed the Remaining Weekly Dose.
 
- Subjects will come to clinic for assessment even if the originally selected wounds are closed.
 
 
Safety Follow-up/Early Termination
 
 
- Subjects will return to the clinical site 30 days following the last dose of B-VEC.
 
- Subjects may roll into an Open Label Extension (OLE) Protocol. If subjects do not participate in the OLE Protocol, they will be asked to roll over into a Long-Term Follow-up Protocol (All subjects enrolled in the study who received at least a Weekly Treatment).
 
 
Assessments
 
 
- Safety measures include adverse events, physical examinations, vital signs, and clinical laboratory tests. All safety analyses results will be performed using the safety population. A summary of safety results will be presented for each treatment group.
 

---	---

Statistical Analyses	
Continuous variables will be summarized in tables and will include the number of subjects, mean, standard deviation (SD), percent of coefficient of variance (CV%), median, minimum, and maximum. Categorical variables will be presented in tables as frequencies and percentages. A statistical analysis plan (SAP) will provide additional details on the approach to the analysis and data displays.
 
Sample Size Estimation
 
In the Phase I/II study, the response rates for Weeks 8 through 12 were from 70-100% for wounds randomized to B-VEC and 0-33% for wounds randomized to placebo, respectively. Assuming a response rate of 75% among wounds randomized to B-VEC and a response rate of 25% among wounds randomized to placebo, with a 90% power and a two-sided Type 1 error rate of 5%, 24 subjects (i.e., 24 wound pairs) are required.
 
Analysis Populations
 
Safety Population:
 
This population is defined as all subjects who were administered with either B-VEC or placebo. Safety population will be used for all the safety analyses.
 
Intent-to-Treat Population:
 
The intent-to-treat (ITT) population includes subjects whose primary wounds were randomized with or without either B-VEC or Placebo administration. ITT population will be used for all the primary and secondary efficacy sensitivity analyses and baseline summaries.
 
Modified Intent-to-Treat Population:
 
The modified intent-to-treat (mITT) population includes subjects whose primary wounds were randomized and received B-VEC treatment with at least one post baseline primary endpoint assessment. mITT population will be used for all the primary and secondary efficacy analyses.
 
Per Protocol Population:
 
The per-protocol (PP) population includes all the safety population subjects who completed the study without major protocol deviations. PP population will be used for all the primary and secondary efficacy sensitivity analyses.
 
Missing Values and Imputations
 
Multiple imputation method will be used to handle missing data for primary efficacy analysis. For all the exploratory endpoints, the missing values will not be imputed.

---------------------------------	--


Statistical Analyses (continued)
	
Efficacy Analyses: The study has a complete randomized-block design in which each subject serves as a block to receive all of the treatment conditions. In this study, each subject provides one pair of matched target wounds with one wound being treated with B-VEC and the other wound with placebo in the primary wound pair. Efficacy measurements are taken multiple times (or repeatedly) over the on-treatment period from each subject. Efficacy measures collected pre-dosing at Visit 1 (Week 1) will be considered as the baseline measurement in this study.
 
Analysis of Primary Efficacy Endpoint: The primary endpoint of the proportion of DEB primary wound sites with complete wound healing of the exact wound surface area selected at baseline will be analyzed using the McNemar Test. The primary endpoint is defined as wounds that meet any of the following conditions:
 
 
• Healed on Week 22 and Week 24, or
 
• Healed on Week 24 and Week 26.
 
 
Only wounds that are healed for at least two (2) consecutive weeks are counted as positive responses.
 
Analysis of Key Secondary Efficacy Endpoint: The key secondary endpoint of the proportion of primary wound sites with complete wound healing of the exact wound surface area selected at baseline, will be analyzed using the McNemar Test. The primary endpoint is defined as wounds that meet any of the following conditions:
 
 
• Healed on Week 8 and Week 10, or
 
• Healed on Week 10 and Week 12.
 
 
Only wounds that are healed for at least two (2) consecutive weeks are counted as positive responses.
 
Analysis of Secondary Efficacy Endpoint: The following secondary endpoint will be analyzed using the Analysis of Covariance (ANCOVA) with treatment as the fixed effect and the baseline value as the covariate by the time points.
 
 
1. The mean change from baseline in pain severity VAS score per wound site associated with wound dressing changes at Weeks 22, 24 and 26 for each treated versus placebo for ages 6 and above on the primary wound pair. For ages below 6 years, the FLACC-R scale scores will be used instead VAS scores.
 
 
Safety Analyses: Safety measures include adverse events, physical examinations, vital signs, and clinical laboratory tests. All safety analyses results will be performed using the safety population. A summary of safety results will be presented for each treatment group.


Long-term follow-up
	
Subjects will be asked to transfer to a long-term follow-up study, which will include up to 5 years of annual phone check-ins. Subjects may roll into the Long-Term Follow-Up Protocol at the Safety Follow-up Visit (30 days following the last dose of B-VEC).

DSMB Reviews
	
A data monitoring board (DSMB) will conduct regular planned safety reviews of study data as outlined in the DSMB charter.

## Schedule of Events

**Table 1. Visit Assessments and Procedures**

Study Day	Randomized-Double Blinded Placebo-Controlled Treatment Period								Safety Follow-up/ET
	Screening 	Week 1	Week 2 -21	Week 22	Week 23	Week 24	Week 25	Week 26	30 days after last dose
Daily Visit Window	-60 to 0	na	± 3 days						± 4 days
Visit	Screening	1	2-21	22	23	24	25	26	SFU
Obtain Consent / Assent	X	X 							
Inclusion/Exclusion Criteria		X							
Demographics	X	X 							
Medical History	X	X 							
Genetic Testing	X 								
Wound Selection		X							
Wound randomization 		X							
Pain Assessment- Wound Pair 		X		X		X		X	
Quality of Life Questionnaire (EQ-5D) 		X						X	
Skindex Questionnaire 		X						X	
Imaging 		X	X	X	X	X	X	X	X
Assessment of Wound Closure 		X	X	X	X	X	X	X	
Swabs for Viral Shedding/Infectivity 		X	X	X	X	X	X	X	
Swabs for Viral Shedding on Dressing Returned 			X						

 If genetic testing is required, this test may occur up to 60 days prior to the other screening procedures, following subject consent/assent. Genetic testing may take 6-8 weeks to obtain results.

 Informed consent/assent, demographics, medical/ procedural history, urine (if male) and blood specimens will not be re-collected, if collected at a Screening visit.

 The matched primary wound pair will be randomized.

 Pain questionnaires are to be completed during the dressing change of the individual matched wounds. If subject is 6 years of age or older, they will be asked to complete the VAS questionnaire for matched wounds during the dressing change. If younger than 6 years of age, their parent/caregiver will be administered the FLACC-R questionnaire for the matched wounds during the dressing change (Refer to section 6.2.2).

 Both the Quality of Life (EQ-5D) and Skindex Questionnaires will be administered to subjects 12 years of age and older at the time of consent. Questionnaires may be administered for the subject to complete after the visit and bring back at the next scheduled visit.

 Images will be collected on both closed and open wounds. Image in the same order and orientation at each visit prior to IP application.

 Primary wound closure assessments will be evaluated by the Investigator only at Weeks 8, 10, 12, 22, 24 and 26. Secondary wound closure is assessed weekly, to determine if a new wound may be selected to receive treatment, if the originally selected area and its neighboring wound/s has closed, as applicable.

 Viral shedding and infectivity swabs will be collected from the primary matched wounds only and will be collected whether or not the wound is open or closed.

 Subjects are required to bring the study visit wound dressing back to the site. Primary wounds will be separately bagged. Secondary wound dressing may be bagged together. Once returned to the site, viral shedding swabs will be collected for all Primary Wounds dressings that came into contact with the subject's skin. Attempt collection of (4) four consecutive VS dressing returns, if unable, collect at least (4) four dressing VS per subject. Once four (4) VS samples have been collected from the Primary Wound Pair, all dressing may be bagged together and returned to the site for disposal and specimen collection will be discontinued.

**Table 2. Visit Assessments and Procedures (continued)**

Study Day	Randomized-Double Blinded Placebo-Controlled Treatment Period								Safety Follow-up/ET
	Screening 	Week 1	Week 2 -21	Week 22	Week 23	Week 24	Week 25	Week 26	30 days after last dose
Daily Visit Window	-60 to 0	na	± 3 days						± 4 days
Visit	Screening	1	2-21	22	23	24	25	26	SFU
Physical Exam 		complete						Abbrev.	Abbrev
Treatment and Procedure Review 	X	X	X	X	X	X	X	X	X
Medication Review 	X	X	X	X	X	X	X	X	X
AE and SAE Review		X	X	X	X	X	X	X	X
Vital Signs 		X	X				X		X
Urine Pregnancy Test 		X						X	
Urine for Viral Shedding 	X	X 						X	
CMP w/Direct Bilirubin 	X	X 						X	
CBC/Diff 	X	X 						X	
COL7 & HSV Serum ADA 	X	X 						X	
Whole Blood Viral Shedding 	X	X 						X	
Investigational Product (IP) Administration 		X	X	X	X	X	X	X	
Roll-over to LTFU or OLE Protocol 									X

10 The Physical examination is described in section 0

11 All medication taken 3 months prior to Screening/Visit 1 through the end of the study will be recorded as well as all applicable procedures and treatments within the last 3 months to Screening/Visit 1.

12 On days in which both vitals and blood draw occur, attempt vitals prior to the blood draw. Vitals are collected every 5 visits (i.e. Visit 1; 5; 9; 13; 17; 21; 25; SFU/ET). Vitals may be obtained more frequently as determined by the Investigator.

13 A urine pregnancy test will be completed on all women of childbearing potential prior to blood collection and drug administration, as determined by the Investigator.

14 For Subjects with history of genitourinary involvement, including painful urination due to the underlying disease and or Subjects who are 4 years of age and younger, are not required to provide a urine sample, as determined by the Investigator. Documentation must be recorded on the CRF and listed in Medical History.

15 Labs will be attempted, unless per the discretion of the Investigator, it is not in the best interest of the subject. If labs are attempted and not obtained, documentation will be noted in the study visit. Furthermore, if labs are not attempted, justification must be recorded in the study visit. The Investigator must determine clinical significance for out-of-range values.

16 Conduct all other study visit procedures prior to B-VEC and placebo administration. Matched Wounds: IP will be applied to wounds that are open. If a matched wound and neighboring wound is closed, no IP will be applied and application will be reinitiated once the wound reopens at a scheduled visit, as determined by the Investigator. Secondary Wounds: IP will only be applied to open wounds as determined by the Investigator, not to exceed the Remaining Weekly Dose. IP may be applied to immediate neighboring wounds. Up to four (4) unmatched Secondary Wounds may be selected to receive open-label B-VEC during the study treatment. Trace the area that is receiving treatment (including the neighboring wounds). Neighboring wounds are defined as wounds approximately 2-3cm away from the original matched and unmatched (Primary and Secondary) wound.

17 At the Safety Follow-up (30 days ± 4 days) following the last dose of B-VEC, subjects may roll over into an OLE protocol or will be asked to roll over into a LTFU protocol

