# Protocol

## 1 Introduction

### 1.1 Disease Background

Dystrophic epidermolysis bullosa (DEB) is a group of heritable skin diseases characterized by skin fragility, blister formation, milia, and scarring (Intong, 2012). Dystrophic epidermolysis bullosa (DEB) is one of the major forms of EB and is the result of mutations to the COL7A1 gene encoding collagen VII (Varki, et al., 2007), (Uitto & Christiano, 1994). Severe generalized recessive dystrophic epidermolysis bullosa, formerly termed Hallipeau-Siemens, is characterized by extensive blistering and scarring of the skin and mucosal membranes. Blisters and erosions affect skin as well as certain mucosa exposed to disruptive external environment, including oropharynx, esophagus, rectum, genitourinary system and eyes. Healing of erosions results in debilitating scarring. Damage to the mouth and esophagus can make it difficult to chew and swallow food, leading to chronic malnutrition and slow growth. Complications from extensive scarring can include fusion of the fingers and toes, joint deformities, and vision impairment. Given the severity of this disorder and the lack of effective treatment options, there exists a clear need for alternative treatment options that focus on the root cause of the debilitating symptoms and can be administered in a minimally invasive way.

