### **3.1 Inclusion Criteria**

To be eligible for inclusion, each subject must fulfill each of the following criteria:

1. The subject or legally appointed and authorized representative must have read, understood and signed an Institutional Review Board/Ethics Committee (IRB/EC) approved Informed Consent or Assent Form and must be able to and willing to follow study procedures and instructions.
2. Age  $\geq$  6 months and older at the time of Informed Consent.
3. Clinical diagnosis of the Dystrophic Epidermolysis Bullosa.

4. Confirmation of DEB diagnosis (either DDEB or RDEB) by genetic testing including COL7A1.
5. Two (2) cutaneous wounds meeting the following criteria:
  - a. Location: similar in size, located in similar anatomical regions, and have similar appearance (Refer to section 5.8 for more details).
  - b. Appearance: clean with adequate granulation tissue, excellent vascularization, and do not appear infected.
6. Subjects and caregivers who, in the opinion of the Investigator, are able to understand the study, co-operate with the study procedures and are willing to return to the clinic for all the required follow-up visits.
7. Male or Female of childbearing potential must use a reliable birth control method throughout the duration of the study and for three (3) months post last dose of B-VEC. Refer to Section 4.5.1 for more details.
8. Negative pregnancy test at Visit 1 (Week 1), if applicable.

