##### **4.5.1 Contraception**

Women of childbearing potential must have a negative urine pregnancy test at the Visit 1 (Week 1) visit and must commit to using an acceptable form of contraception during the entire study period, up to three (3) months following the last dose of B-VEC. Acceptable forms of contraception include abstinence, intrauterine device, oral, implantable, or injectable contraception, or a combination barrier method, such as female or male condom, a diaphragm or cervical cap and a spermicide. Women using oral contraception must have consistently been taking their birth control for three (3) months prior to Visit 1 (Week 1) or utilize a combination barrier method, as stated above.

Male subjects must be surgically sterile, prepubescent or agree to use (you or your childbearing partner) an effective form of contraception from Visit 1 (Week 1) to three (3) months following study completion (last dose of B-VEC), such as abstinence, intrauterine device, oral, implantable or injectable contraception, or a combination barrier method, such as female or male condom, a diaphragm or cervical cap and a spermicide.

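### Footnote 14 excuses subjects with genitourinary involvement from the urine pregnancy test without excepting women of childbearing potential, in conflict with Protocol section 4.5.1

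*Protocol*

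**What the plan says.** The Urine Pregnancy Test row in Protocol Table 2 (Visit Assessments and Procedures, continued) schedules the test at Week 1 and Week 26 and carries two footnote markers, 13 and 14. The schedule in SAP Appendix 1 repeats the row and both notes.

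- Footnote 13 says a "urine pregnancy test will be completed on all women of childbearing potential prior to blood collection and drug administration, as determined by the Investigator".
- Footnote 14 says that subjects with a history of genitourinary involvement, painful urination included, and subjects aged 4 and younger "are not required to provide a urine sample, as determined by the Investigator". Its one condition is "Documentation must be recorded on the CRF and listed in Medical History".
- Section 4.5.1 says "Women of childbearing potential must have a negative urine pregnancy test at the Visit 1 (Week 1) visit". It has no qualifier and no exception.
- Section 3.1 opens by saying that "each subject must fulfill each of the following criteria", and criterion 8 reads "Negative pregnancy test at Visit 1 (Week 1), if applicable". The synopsis copy ("Negative Pregnancy test on Visit 1 (Week 1), if applicable") has the same effect. Neither names a specimen.
- Sections 4.2.1 and 6.3.4.2 each call for a negative urine result before study product is applied at the visits where the test is scheduled. Both end with the same reference to the Investigator's determination as footnote 13.

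**The concern.** A footnote on a pregnancy-test row removes the specimen that the test needs, and it does so for a group that includes women who could be pregnant. Followed as printed, it cancels a test that section 4.5.1 makes mandatory. A site with such a patient has no text telling it which provision to follow.

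The group is foreseeable. Section 1.1 describes blisters and erosions of mucosa in severe generalized recessive disease, "including oropharynx, esophagus, rectum, genitourinary system and eyes". Pregnancy is an exclusion under section 3.2, and section 6.10.2 requires a subject who becomes pregnant to leave the study at once, so the protocol clearly intends to know pregnancy status before dosing. The contraception requirements lower the risk, but the protocol asks for a test in addition to them.

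**Working it through.** No power, alpha or sample-size figure is involved. The check is a comparison of texts.

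**1. Where the waiver applies.** Marker 14 appears on the Urine Pregnancy Test row and on no other row in either document. The Urine for Viral Shedding row carries marker 15 only. Children aged 4 and younger do not need a pregnancy test, so on this row the waiver has practical effect mainly for women of childbearing potential with genitourinary involvement.

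**2. What it collides with.**

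| Place | Visit | Requirement | Qualifier |
|---|---|---|---|
| 4.5.1 | Week 1 | Negative urine test | None |
| Table 2, footnote 13 | Weeks 1 and 26 | Urine test in all women of childbearing potential | Investigator determines |
| 4.2.1 | Scheduled test visits | Negative urine test before product | Investigator determines |
| 6.3.4.2 | Specified visits | Negative urine test before invasive procedures and product | Investigator determines |
| 4.2.4 and 4.2.10 | Weeks 1 and 26 | Urine collected for the test | Where applicable, Investigator determines |
| 3.1, criterion 8 | Week 1 | Negative test, specimen not named | Where applicable |

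The conflict with 4.5.1 does not depend on interpretation. For footnote 13, 4.2.1 and 6.3.4.2 it depends on what the Investigator determines. If that is whether to test, these statements leave room for the waiver. If it is who is of childbearing potential, they are firm requirements and conflict with footnote 14. Because 4.2.1 and 6.3.4.2 apply wherever the test is scheduled, and product is still given at Week 26, the conflict then covers both visits.

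**3. Whether a substitute is scheduled.** The blood lists at Screening, Week 1 and Week 26 name the same four items: metabolic panel, blood count, HSV and COL7 antibodies, and whole blood for viral shedding. The two panels in section 6.3.4.1 list 16 + 14 = 30 analytes, none of them a pregnancy test. Scheduled non-urine pregnancy tests: 0.

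**4. Scheduled tests for a woman with genitourinary involvement.**

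- Excused under footnote 14 at both visits: 2 − 2 = 0.
- Under 4.5.1: at least 1 (Week 1).
- Under footnote 13, 4.2.1 and 6.3.4.2, read as firm: 2.

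**5. How many women.** The planned total is about 24 subjects. The documents give neither the number of women of childbearing potential nor the share with genitourinary involvement, so no count can be derived.

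**The case against.** The strongest reply is that footnote 14 excuses a urine sample, not a pregnancy test. Eligibility is set elsewhere: section 3.1 binds every subject to every criterion, criterion 8 asks for a negative result without naming urine, and pregnancy is an exclusion. Read together, a woman who gives no urine is tested another way or is not enrolled. Much of this stands. A reader might infer that the plan permits dosing women whose pregnancy status is unknown. The documents do not support that, because a site would have to let a schedule footnote override both 4.5.1 and criterion 8. What remains is that no text states the order of precedence, no alternative test is provided, and a careful site that used a blood test would still miss the wording of 4.5.1, which specifies urine.

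A reader might also infer that 4.5.1 is the only firm requirement, and so that the problem is confined to Week 1. That takes one side of an ambiguity. The references to the Investigator's determination, and the applicability wording in criterion 8, can equally mean identifying who could be pregnant.

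Footnotes 13 and 14 share a row and could be read as rule and exception. That reading does not reach 4.5.1.

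Finally, marker 14 may be misplaced. Its age exemption makes little sense for a pregnancy test and good sense for viral-shedding urine. Footnote 2 of the schedule spares only male subjects from repeat urine collection at Week 1, so the default is that women give urine then. This is plausible, but it is inference, and it does not correct the printed table in either document.

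**Conclusion.** The concern holds as a narrow safety inconsistency. As printed, footnote 14 conflicts with section 4.5.1 at Week 1. It also conflicts with footnote 13 and sections 4.2.1 and 6.3.4.2, at Week 26 as well, on the assumption that the Investigator's determination there concerns childbearing potential. The size is up to 2 of 2 scheduled pregnancy tests removed for each woman excused, with none scheduled in their place. The number of such women is unknown. Criterion 8 and section 3.1 weigh against an untested woman being dosed, and the point does not bear on the endpoints, type I error, power or any efficacy analysis. It merits correction because the gap is in a safety check and closing it is easy.

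**What to change.** Add one sentence to footnote 14 and to its copy in SAP Appendix 1: the exemption does not waive the pregnancy test for women of childbearing potential, who must have a negative result at each scheduled test visit (Weeks 1 and 26) before dosing. If the sponsor confirms that marker 14 was misplaced, moving it to the Urine for Viral Shedding row in both documents is an alternative.

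Optionally, accept a non-urine test at either visit for women who cannot give urine. This takes more than one sentence:

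- 4.5.1 and 4.2.1 would have to stop specifying urine alone.
- Footnote 2 would have to exclude this test, since blood taken at Screening, up to 60 days before Week 1, is not drawn again.
- Footnote 15 would have to exclude it, since laboratory draws are discretionary.
- Footnote 13 and 6.3.4.2 would have to exempt the draw itself, since they place the test before blood collection or any invasive procedure.

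The main fix costs one sentence in two places. Its downside is that a few women with painful urination must give urine or, under the optional route, another specimen. That gives back a little of what Version 1.2 gained by minimizing urine collection and phlebotomy. The optional route also adds an assay for each woman who uses it.
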